5.4.2 Online Registration

Patients can be registered only after eligibility criteria are met.

Special assistance for institutions from China can be obtained from the following web site: <http://www.rtog.org/ClinicalTrials/RTOGFoundationStudies/RTOGFoundationStudy3502.aspx>

Each individual user must have an RTOG user name and password to register patients on the RTOG web site. To get a user name and password:

- The investigator and research staff must have completed Human Subjects Training and been issued a certificate (Training is available via <http://phrp.nihtraining.com/users/login.php>).
- A representative from the institution must complete the Password Authorization Form (<http://www.rtog.org/LinkClick.aspx?fileticket=-BXerpBu5AQ%3d&tabid=219>) and fax it to [contact]. RTOG Headquarters requires 3-4 days to process requests and issue user names/passwords to institutions.

An institution can register the patient by logging onto the RTOG web site (<http://www.rtog.org>), going to "Data Center Logon" and selecting the link for new patient registrations. The system triggers a program to verify that all regulatory requirements (OHRP assurance, IRB approval) have been met by the institution. The registration screens begin by asking for the date on which the eligibility checklist was completed, the identification of the person who completed the checklist, whether the patient was found to be eligible on the basis of the checklist, and the date the study-specific informed consent form was signed.

Once the system has verified that the patient is eligible and that the institution has met regulatory requirements, it assigns a patient-specific case number. The system then moves to a screen that confirms that the patient has been successfully enrolled. This screen can be printed so that the registering site will have a copy of the registration for the patient's record. Two e-mails are generated and sent to the registering site: the Confirmation of Eligibility and the patient-specific calendar. The system creates a case file in the study's database at the DMC (Data Management Center) and generates a data submission calendar listing all data forms, images, and reports and the dates on which they are due.

If the patient is ineligible or the institution has not met regulatory requirements, the system switches to a screen that includes a brief explanation for the failure to register the patient. This screen can be printed.

Institutions can contact RTOG web support for assistance with web registration: [contact].

In the event that the RTOG web registration site is not accessible, participating sites can register a patient by calling RTOG Headquarters, at [contact], Monday through Friday, 8:30 a.m. to 5:00 p.m. ET. The registrar will ask for the site's user name and password. This information is required to assure that mechanisms usually triggered by web registration (e.g., confirmation of registration and patient-specific calendar) will occur.

6.0 RADIATION THERAPY

Note: All participating institutions will be credentialed for a dry-run case, phantom irradiation, IGRT, and 3DCRT (or IMRT, if used) as described in Section 5.1 prior to registering patients to the study. Centers not credentialed for IMRT are not permitted to enroll and treat patients with this approach.

Protocol treatment must begin within 14 calendar days after randomization.

The protocol procedures associated with SBRT will respect updated guidelines set by ACR/ASTRO [182].

6.1 Simulation/Immobilization

6.1.1 Positioning/Immobilization

The patient will be scanned in the supine position with both arms raised above the head to allow beams from multiple directions. Securing a comfortable position is critical as it allows accurate reproducibility of the target localization from treatment to treatment. Uncomfortable positions should be avoided as they will most likely cause uncontrolled movement during scanning or treatment. A variety of immobilization systems may be used, including vac-bag, alpha cradle, and stereotactic frames. While frames are intended to index the patient to a stereotactic coordinate, their use alone (i.e. without image guided positioning) is insufficient for this trial.

Immobilization should be sufficient to maintain the intra-fraction patient position (tumor and adjacent skeletal) to within 3 mm. A post-treatment verification image should be taken to document the intra-fraction error for set up. The comparison between these images with reference images should be quantitatively analyzed and must not be > 5 mm. The institution should store these datasets on site for possible review/audit by the Principal Investigators.

6.1.2 CT Simulation and Motion Management

Target motion will be managed appropriately to ensure target localization and reproducibility. Tumor motion will be assessed by using fluoroscopy, 3-phase CT scanning or optimally 4D-CT scanning of 10 breathing phases. For CT scanning, intravenous contrast is not mandatory. If IV contrast is used, CT images without IV contrast should also be acquired and used for dose calculations. The slice spacing between reconstructed CT images should be ≤ 3 mm encompassing the entire lung volume.

An internal target volume (ITV) approach can be used up to a limit of 1.5 cm movement in one direction.

When the tumor motion is more than 1.5 cm in any one direction, as demonstrated using one of the techniques described above, special measures should be applied to reduce internal organ motion. Acceptable maneuvers for motion control include reliable abdominal compression, accelerator beam gating with the respiratory cycle, tumor tracking using fiducial markers, and active breath-holding techniques. Regardless of the tumor motion management method applied, image guidance for target localization is required for initial positioning at the start of each treatment fraction.

6.1.3 Localization/Verification

Localization images or Cone Beam CT (CBCT) should be obtained at each treatment on the treatment unit. ITV from 3D CBCT should be compared to the ITV from the planning CT. 4DCBCT also can be used for target verification, if available, but it is not required. These images should be taken immediately before treatment to ensure proper alignment of the geometric center (i.e., isocenter) of the simulated fields. Verification images (3D) should be taken if more than 3 mm shifts are performed before treatment, as indicated by image guidance and after treatment to document the patient positioning accuracy.

6.1.4 SBRT Dose Fractionations

SBRT is given every other day. A total dose of 55 Gy will be given in 5 fractions within 10-15 days with an inter fraction interval of 2-3 days. The dose for all patients will be prescribed to the isodose line that covers 95% of the PTV. Treatment duration up to 20 days is permitted to allow for circumstances such as holidays or unanticipated medical conditions. Tissue heterogeneity corrections must be applied for dose calculation using convolution/superposition calculation techniques or a Monte Carlo algorithm. Planes should be normalized to provide 95% coverage of the planning target volume with the prescription dose. Dose constraints are provided in Tables 6a and 6b.

6.1.5 SBRT Target Delineation

The gross tumor volume (GTV) will be delineated by an appropriately trained physician using CT pulmonary windows for tumor surrounded by lung parenchyma. Soft tissue windows should be used for tumors adjacent to chest wall, or centrally located IV contrast may be used to avoid inclusion of adjacent vessels or chest wall structures within the GTV. The correctness of the GTV delineation should be checked in axial, sagittal and coronal views. **This target will not be enlarged whatsoever for prophylactic treatment (including no “margin” for presumed**

microscopic extension); rather, include only an abnormal CT signal consistent with gross tumor (i.e. the GTV and the clinical target volume [CTV] are identical). An additional 0.5 cm in the axial plane and 1.0 cm in the longitudinal plane (craniocaudal) will be added to the GTV to constitute the PTV.

As an alternative, sites equipped with 4D CT scanning equipment may generate an Internal Target Volume (ITV) using the inspiration and expiration images or maximum intensity projections (MIP) as appropriate. Sites should be aware that the MIP reconstruction may erroneously define an ITV in cases of significant irregular breathing or when tumors abut soft tissue structures (e.g. the diaphragm, great vessels). The 4D scan acquired for planning, however, should be obtained after initial assessment of tumor motion confirming that the tumor motion will be no greater than 0.5 cm in the axial plane and 1.0 cm in the craniocaudal plane. If 4D CT is not available, the composite GTV should be based on either the CT data covering the whole tumor trajectory taken over multiple breathing cycles or the summation of GTVs drawn on multiple rapid planning scans. Regardless of the method of ITV generation, if a PET scan is also acquired, the PET target should be compared to the ITV to ensure sufficient target size for coverage of the moving tumor. In general, an ITV should NOT be defined by the merger of a deep inspiration CT scan and a deep expiration CT scan, as such would typically overestimate tumor motion. The ITV, then, is generated using a CT dataset where motion control maneuvers are already successfully employed. This ITV can be expanded by the institution's geometric set-up uncertainty (e.g. 4-5 mm) to generate the PTV.

6.2 Delineating Organs at Risk and Dosimetric Limits (6-AUG-2018)

Please see the atlas on the RTOG web site, www.rtoq.org, on the page for RTOG 1106. All required structures must be named according to naming convention provided on RTOG website. See list available at

<http://www.rtoq.org/ClinicalTrials/RTOGFoundationStudies/RTOGFoundationStudy3502.aspx>

6.2.1 Lung

Lung contours should be limited to active alveolar regions without inclusion of fluid and atelectasis. Automated contouring tools may be used but appropriate thresholds, specific to each CT scan, should be chosen. Editing of autotracked contours is always required. The proximal bronchial tree should be excluded, and small sized vessels (less than 1cm, or vessels beyond the hilar region) should be included. The right and left lungs should be contoured as separate structures, and the DVH of whole lung should be generated by inclusion of both lungs. Normally the lung dose limits are based on the DVHs of both lungs with exclusion of composite GTV. Special attention should be paid that only the GTV overlapping normal lungs is subtracted (i.e., only the component of the GTV existing within the lung); the GTVs outside of lung such as the mediastinal nodal GTVs should not be subtracted. All inflated and collapsed lung should be contoured; trachea/ bronchus as defined below should not be included in this structure. When there is collapsed lung, the use of IV contrast and/or PET scanning may be very helpful at distinguishing collapsed lung from tumor extension.

6.2.2 Proximal Tracheal Bronchial Tree

The proximal bronchial tree should be contoured using mediastinal windows on CT to correspond to the mucosal, submucosa and cartilage rings and airway channels associated with these structures. The proximal tracheal bronchial tree should be contoured as one structure, should include the most inferior 2 cm of distal trachea and the proximal airways on both sides. The following airways should be included according to standard anatomic relationships: the distal 2 cm of trachea, the carina, the right and left mainstem bronchi, the right and left upper lobe bronchi, the intermedius bronchus, the right middle lobe bronchus, the lingular bronchus, and the right and left lower lobe bronchi. Contouring of the lobar bronchi should end immediately at the site of a segmental bifurcation, as recommended by RTOG 0618.

6.2.3 Esophagus

The esophagus should be contoured using mediastinal windowing on CT to correspond to the mucosal, submucosa, and all muscular layers out to the fatty adventitia. The esophagus should be contoured starting at the level of cricoid and continuing on every CT slice to the gastroesophageal junction.

6.2.4 Spinal Cord

For specifically treating lung tumors, the spinal cord should be contoured based on the bony limits of the spinal canal. The spinal cord should be contoured starting at the same cranial level as esophagus to L2, when the cord ends. RTOG studies recommend at least 10 cm above the superior extent of the PTV and continuing on every CT slice to at least 10 cm below the inferior extent of the PTV, as such definition may go beyond the true cord ends for inferior tumors.

6.2.5 Ribs and Chest Wall

Delineation of ribs and chest wall will be contoured by using corrected lung contours with a 2 cm expansion at lateral, anterior and posterior directions. Intercostal muscles are to be included, while other muscles and skin are excluded. This is a result of combined consideration of previous methods of including ribs alone or comprehensive inclusion of the chest wall [185, 186]. One can also confine the rib contours to the relevant tissue that exists within a 3 cm range from the PTV.

6.2.6 Brachial Plexus

The brachial plexus originates from the spinal nerves exiting the spinal canal through the neural foramina from the C4/5 (C5 nerve roots) to the T1/2 (T1 nerve roots) level. Using high quality CT scanning with IV contrast, it is possible to identify the actual roots and trunks of the brachial plexus directly with no need of a surrogate. We recommend outlining this structure starting from C5 root (within the C4/5 neural foramen) and ending at the subclavian neurovascular bundle without including the vessels. To contour the brachial plexus correctly, it is critical to first identify the anterior and middle scalene muscles, the subclavian and axillary arteries and veins, and relevant cervical and thoracic vertebrae on axial CT.

6.2.7 Heart/Pericardium

The heart will be contoured along with the pericardial sac. The superior aspect (or base) for purposes of contouring will begin at one slice below the level of the inferior aspect of the pulmonary artery trunk crossing the midline and extend inferiorly to the apex of the heart.

6.2.8 Skin OAR

The skin will be defined as the outer 0.5 cm of the body surface. As such it is a rind of uniform thickness (0.5 cm) which envelopes the entire body in the axial planes. The cranial and caudal surface of the superior and inferior limits of the planning CT should not be contoured as skin unless skin is actually present in these locations (e.g., the scalp on the top of the head).

6.2.9 Great Vessels

The great vessels (aorta and vena cava, not the pulmonary artery or vein) will be contoured using mediastinal windowing on CT to correspond to the vascular wall and all muscular layers out to the fatty adventitia. The great vessel should be contoured starting at least 10 cm above the superior extent of the PTV and continuing on every CT slice to at least 10 cm below the inferior extent of the PTV. For right sided tumors, the vena cava will be contoured, and for left sided tumors, the aorta will be contoured.

6.2.10 Structures are to be labeled exactly according to the "Standard DICOM Name" in the left column of the table below. Additional structures will be deleted and if any missing structures are noted, the case will be requested for resubmission.

STANDARD DICOM NAME	Description
GTV	Gross Tumor Volume
ITV	Internal Target Volume
PTV	Planning Target Volume
PTV_20	PTV + 2cm
Lung_R	Right Lung
Lung_L	Left Lung
Lungs	(Right + Left Lung) minus GTV
BronchialTree	Proximal Bronchial Tree
BroncTree_20	Proximal Bronchial Tree + 2cm
Esophagus	Esophagus
SpinalCord	Spinal Cord
Rib	Ribs & Chest Wall
BrachialPlexus	Brachial Plexus
GreatVessels	Great Vessels
Heart	Heart & Pericardium
SkinOAR	Skin (outer .5cm rind)

SkinOAR-PTV	Skin (outer 0.5 cm rind) minus PTV
SkinOAR-PTV_20	Skin (outer 0.5 cm rind) minus PTV_20
External	Entire Body/External Contour
External-PTV	External Contour minus PTV
External-PTV_20	External Contour minus PTV_20
Trachea	Trachea

6.3 Radiation Planning/Dose Conformality Requirements (9/12/13)

6.3.1 General Guidelines

The dose to the target should be maximized while the dose to the adjacent OARs minimized. Both co-planar and non-coplanar beam arrangements are allowed. All dose calculations and Monitor Unit calculations should include tissue heterogeneity corrections as available in the planning system based on the CT data. A superposition/convolution algorithm or better is required. Photons of 6 MV to 10 MV will be allowed to optimize the dose plan. 10 MV photons only will be used when there is adequate soft tissue before the tumor at the beam entrance direction.

Dose calculations should be performed on the 3D CT scan reconstruction generated without breathing phase binning (i.e. an average scan or untagged scan reconstruction).

A hot spot is allowed within the ITV. The prescription isodose line shouldn't be below 60% as specified in Section 6.3.4.

Successful treatment planning will require accomplishment of all of the following criteria:

6.3.2 Normalization

An initial treatment plan used to select the isodose line for PTV coverage should be normalized such that 100% corresponds to the center of mass of the PTV. This point will typically also correspond (but is not required to correspond) to the isocenter of the treatment beams.

6.3.3 Prescription Isodose Surface Coverage

The dose prescription will be chosen such that 95% of the target volume (PTV) receives the prescribed dose of 55 Gy, and 99% of the target volume (PTV) receives a dose that does not fall below a minimum dose that is defined as 90% of this dose, 99% of ITV and 100% of composite GTV should receive the prescribed dose.

6.3.4 Target Dose Heterogeneity

The prescription isodose surface selected using the initial plan must be $\geq 70\%$. It is preferred to keep the max dose to a 30% maximum increase of the dose at the center of mass (COM) of the PTV and $\leq 90\%$ of the dose at the center of mass of the PTV. The COM_{PTV} corresponds to the normalization point (100%) of the plan.

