6.3.5 Hot Spot Consideration

- a) **Location:** Any dose $> 105\%$ of the prescription dose should occur primarily within the PTV itself and not within the normal tissues outside the PTV.
- b) **Volume:** Conformality of PTV coverage will be judged to meet criteria in Sections 6.3.2 to 6.3.5, with ratio of the volume of the prescription dose to the volume of the PTV is ideally < 1.2 (see table below). These criteria will not be required to be met in treating very small tumors (< 2.5 cm axial GTV dimension or < 1.5 cm craniocaudal GTV dimension) in which the required minimum field size of 3.5 cm results in the inability to meet a conformality ratio of 1.2.

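### Section 6.3.4 limits the maximum SBRT dose to both 130% and 90% of the same center-of-mass dose, which is itself the 100% point, so the 90% clause cannot be met as written

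*Combined protocol and SAP*

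**What the plan says.** The relevant text is in Section 6.3 of the protocol.

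- **Prescription (6.3.3).** The dose is chosen so that "95% of the target volume (PTV) receives the prescribed dose of 55 Gy".
- **Reference point (6.3.2).** The initial plan is "normalized such that 100% corresponds to the center of mass of the PTV". Section 6.3.4 repeats that this point "corresponds to the normalization point (100%) of the plan".
- **Isodose floor (6.3.4).** The prescription isodose surface must be at least 70%.
- **Maximum dose (6.3.4).** The next sentence reads "It is preferred to keep the max dose to a 30% maximum increase of the dose at the center of mass". It then adds, joined by a plain conjunction and with no new subject, a limit of at most 90% of the dose at that same point.
- **Status (6.3.1).** The general guidelines end by saying that successful planning requires every criterion that follows to be achieved. Section 6.3.5 judges PTV coverage against Sections 6.3.2 to 6.3.5, which takes in 6.3.4.
- **A second floor (6.3.1).** The prescription isodose line should not be below 60%, and Section 6.3.4 is cited as the source of that figure.

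**The concern.** Grammatically, both percentages in the 6.3.4 sentence apply to the maximum dose, and both are taken relative to the COM dose. One of them asks for a plan whose maximum is lower than the dose at a point within that plan.

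This is an operative planning criterion. Section 5.2.4 requires sites to plan the dry-run case strictly to the protocol, and Section 6.6 provides for continuing radiotherapy quality assurance review. A planner or reviewer who reaches this sentence has to decide what the 90% refers to and whether the sentence binds at all. The five institutions mentioned in Section 13.4 could decide differently. What is at stake is a clear limit on the maximum dose inside the target, because no other sentence gives that limit as a number.

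**Working it through.** The plan states no resulting dose figure here that could be reproduced. The check is one of feasibility, followed by simple arithmetic.

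**Inputs.** Prescribed dose 55 Gy (6.3.3). COM = 100% (6.3.2, 6.3.4). Isodose floor 70% (6.3.4) or 60% (6.3.1). Maximum-dose clauses 130% and 90% of the COM dose (6.3.4).

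**Step 1: literal reading.** The COM is a point in the plan, so maximum dose ≥ 1.00 × COM dose. The sentence asks for maximum dose ≤ 1.30 × COM dose and maximum dose ≤ 0.90 × COM dose. The first clause can be met. The second contradicts the starting inequality, so no plan satisfies both.

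**Step 2: size in Gy.** If the prescription isodose is a fraction p of the COM dose, then COM dose = 55/p.

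| Prescription isodose p | COM dose, 55/p | 130% clause | as % of 55 Gy | 90% clause |
|---|---|---|---|---|
| 0.60 (floor in 6.3.1) | 91.67 Gy | 119.17 Gy | 216.7% | 82.50 Gy |
| 0.70 (floor in 6.3.4) | 78.57 Gy | 102.14 Gy | 185.7% | 70.71 Gy |
| 0.90 | 61.11 Gy | 79.44 Gy | 144.4% | 55.00 Gy |

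In every row the 90% clause lies below the COM dose itself.

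**Step 3: an alternative reading.** Suppose the 90% is a ceiling on the prescription isodose surface and the 130% alone applies to the maximum. The isodose then runs from 70% to 90% and the COM dose from 61.1 to 78.6 Gy, which is feasible. If there is no such ceiling, p can in principle rise to 1.0, where the COM dose is 55 Gy. The text does not attach the 90% to the isodose surface, so this reading is an inference.

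**Step 4: the floor.** Moving from 70% to 60% raises the implied limit on the COM dose by 91.67 − 78.57 = 13.10 Gy, and the 130% limit by 119.17 − 102.14 = 17.03 Gy.

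**Step 5: what is untouched.** Doses above 105% of prescription (1.05 × 55 = 57.75 Gy) "should occur primarily within the PTV itself and not within the normal tissues outside the PTV" (6.3.5). The limits at 2 cm from the PTV and on the 50% isodose volume (Table 6a) and the organ-at-risk limits (Table 6b) do not depend on the defective sentence.

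**The case against.** The strongest reply is that little turns on the sentence. It states a preference, so an unattainable clause need not fail any plan. The deviation grading in Table 6a contains no in-target maximum. The 130% clause works alone, the 70% floor is mandatory, and coverage, the dry-run case, the phantom study and central plan review are set out elsewhere. Most of this stands and limits the point to a wording defect. It does not make the 90% clause meaningful. Nor does it settle whether the sentence binds, since Section 6.3.1 places it among criteria that must all be met. Section 6.3.5 also uses non-binding language under that same statement, which shows that the mix is not confined to one sentence but does not resolve it.

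A reader might also infer three stronger things that the documents do not support.

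- **That the hot-spot rules conflict.** Section 6.3.1 says "A hot spot is allowed within the ITV", while 6.3.5 speaks of the PTV. Under Section 6.1.5 the ITV is expanded to make the PTV, so it lies inside it. Section 6.3.1 does not restrict hot spots to the ITV, and one plan can satisfy both.
- **That SBRT is not one treatment across centers.** Prescription and coverage are fixed in 6.3.3. The 70% to 90% reading already allows a COM range of 61.1 to 78.6 Gy, wider than the 55 to 61.1 Gy added by having no ceiling. The 55 Gy end is a mathematical limit; no plan there has been shown to meet Table 6a.
- **That tumor control or bronchial injury is affected.** Section 1.2.1 reports no significant difference between regimens for tumors under 3 cm once BED exceeds 100 Gy, and Section 3.2.2 excludes tumors over 3 cm. Even a COM dose of 55 Gy in 5 fractions gives 55 × (1 + 11/10) = 115.5 Gy, assuming an alpha/beta of 10 Gy (Section 1.4 states 118 Gy). Section 6.7.2 links bronchial injury to large fraction sizes, not to this maximum.

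**Conclusion.** The defect is certain on the text: the 90% clause cannot be met by the quantity it is attached to, and its sentence is the only place that gives the in-target maximum as a number. Whether the sentence is mandatory or preferred is also unclear.

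It would be wrong to conclude that the SBRT arm has no usable upper dose bound. The 70% floor alone holds the COM dose to 78.6 Gy, and the 130% clause taken alone holds the maximum to 102.1 Gy at that isodose. Under the 60% floor in Section 6.3.1 the corresponding figures are 91.7 and 119.2 Gy, which is why the two floors belong in the same correction.

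These figures assume that the prescription isodose is expressed as a percentage of the COM dose, as Sections 6.3.2 and 6.3.4 indicate. They show the effect of each reading and do not say which is right. The sample size and the primary analysis are not affected.

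**What to change.** The sponsor should reconcile Sections 6.3.1 and 6.3.4 in one edit:

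1. Tie each percentage in 6.3.4 to one named quantity, either the prescription isodose surface or the maximum dose, and state the reference dose for each.
2. Mark each limit as mandatory or preferred, consistently with the closing statement of 6.3.1.
3. Make the isodose floor agree between 6.3.1 (60%) and 6.3.4 (70%).

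No value is proposed here; the investigators set them. The cost is a change of protocol wording, with no change to the statistical design.
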